### **3.4. Baseline Variables and Covariates**

For all the primary and secondary functional endpoints, the baseline is defined as the last pre-dose assessment which is collected at the baseline visit.

Subjects will be stratified into two groups based on their ability to complete the 4 stair climb in  $\leq 8$  seconds or  $> 8$  second at baseline. This stratification factor may be used as a covariate in the statistical model when modeling data other than the 4 stair climb. For the 4 stair climb analysis, the actual baseline value instead of the stratification factor will be included in the model. The baseline value may also be included as a covariate in the model for the other functional, strength, or imaging assessments.

Additional covariates including the qualitative assessment for the 4SC will be summarized over time and may be explored in the modeling of the 4SC statistical analysis.

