### 1.10. Study Design Rationale

The four stair climb (4SC) has been selected as the primary endpoint for this study based on results of prior oral steroid clinical trials in DMD. The 4SC has been measured for more than 20 years in DMD, widely used as an outcome in clinical trials, deemed as a reliable measure of motor function (Bushby et al 2011; McDonald et al 2013), can be “bench-marked” by a meaningful improvement with steroids (Manzur et al, 2008) and is a meaningful indicator of DMD boys’ lower limb function in a one year study.

Oral steroids are the only treatment demonstrated in randomized controlled trials to improve DMD boys’ strength and function. (Griggs et al 1991; Mendell et al, 1989). Functional improvements were measured as the time required to walk or run 9 meters or to climb 4 stairs after six months of daily steroids. In a pooled analysis of three separate steroid studies, the magnitude of six month functional improvement compared to placebo group was larger as measured by the stair climb test (-3.69 sec 95% CI [-4.71 to -2.67 sec]) than the walk/run test (-2.64 sec 95% CI [-3.70 to -1.58]) (Manzur et al, 2008). Clinically, propelling oneself up stairs requires more proximal leg strength than walking on a flat surface. This is supported by the natural history of DMD in that boys lose the ability to climb stairs prior to the loss of ambulation (Bushby et al, 2011; McDonald et al, 1995). In addition, there is data to support that a prolonged 4SC >8 seconds time is associated with loss of ambulation in 12 months (McDonald et al, 2013). There is a stronger correlation between knee extensor strength, a key lower limb muscle to maintain ambulation, and 4SC ( $r=0.74$ ) than time to walk/run ( $r=0.70$ ) and distance walked in six minutes ( $r=0.64$ ) (McDonald et al, 2013). A recent industry sponsored trial from PTC Therapeutics (placebo group) demonstrated that DMD boys treated with steroids and  $\geq 7$  years of age demonstrated a mean change of 4.7 sec  $\pm 7.5$  sec over 12 months (McDonald et al, 2013). Therefore, ability to improve time to climb 4 stairs in a 12 month study while boys receive standard of care steroid treatment is a pertinent functional endpoint.

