#### **9.1. Sample Size Determination**

The sample size is based on the primary endpoint of demonstrating efficacy of change from baseline on a 4 stair climb timed function test as compared to placebo at 49 weeks. To detect a 2.5 second difference in change from baseline in 4 stair climb based on a difference between the active treatment and the placebo treatment in Period 1 assuming a common

standard deviation of 4.0 with 80% power at  $\alpha=0.05$  (two-sided), a 2:1 treatment allocation and one interim analysis a total of 96 subjects should complete 49 weeks of dosing for this assessment. Assuming a 10% attrition rate, approximately 105 subjects should be enrolled (70 subjects receiving PF-06252616 and 35 subjects receiving placebo) in order to ensure sufficient number of subjects will complete this assessment. If there are no safety issues and enrollment has completed, additional subjects may be enrolled prior to the time of the interim analysis. These additional subjects may help off-set any unforeseen variability that may occur outside the presumed standard deviation for this age group.

One interim analysis is planned to evaluate futility and efficacy after approximately 50% of the subjects have completed through Week 49. Alpha- and beta-spending functions will be used to determine the cutoffs for efficacy and futility at the interim based on the observed number of subjects in the interim analysis. The gamma family spending functions will be used to appropriately account for error spending and adjust for the observed information at the time of the interim analysis and conservative boundaries ( $\gamma \leq -1$ ) will be used to define the futility and efficacy boundaries. The cutoff used at the interim analysis will be calculated based on the percentage of subjects included at the interim analysis to ensure appropriate protection of the type I error. Further details regarding the interim analysis and simulations are included in the SAP.

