## 5. GENERAL METHODOLOGY AND CONVENTIONS

### 5.1. Hypotheses and Decision Rules

The assumed null and alternative hypotheses for testing the active treatment versus the placebo on the 4 stair climb are included below:

$$H_0: (\mu_{\text{active, 49 weeks}} - \mu_{\text{active, baseline}}) - (\mu_{\text{placebo, 49 weeks}} - \mu_{\text{placebo, baseline}}) = 0$$

$$H_1: (\mu_{\text{active, 49 weeks}} - \mu_{\text{active, baseline}}) - (\mu_{\text{placebo, 49 weeks}} - \mu_{\text{placebo, baseline}}) > 0$$

The primary efficacy analysis will be tested at  $\alpha=0.025$  (one-sided). The same type 1 error rate will be used for testing the secondary analyses. This test will be performed based on the data in period 1 from all subjects. Subjects assigned to sequence 1 and sequence 2 will be analyzed together in an active treatment group compared to subjects in sequence 3 (placebo during period 1).

The decision criteria for the interim analysis is described in CCI

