## 6. ANALYSES AND SUMMARIES

### 6.1. Primary Endpoint

#### 6.1.1. Primary Analysis

The primary endpoint, change from baseline in 4 stair climb, will be analyzed based on the FAS using the mixed effects model outlined in [Section 5.2](#). For primary efficacy analysis, besides FAS, PPAS will be used to assess the sensitivity of the analysis results. These analyses will be performed based on the data for all subjects through 49 weeks. Subjects in sequence 1 and 2 will be combined for analysis purposes and compared to the placebo subjects in sequence 3. Covariates for this analysis include the time to climb 4 stairs at baseline, treatment, visit and treatment by visit interaction. Model estimates and change from placebo estimates, 95% two-sided confidence intervals, and p-values will be displayed for study interpretation purposes. Model estimates with confidence intervals will also be displayed graphically. Graphical summaries of the raw data, including boxplots, will be created to highlight outliers and other influential observations.

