baseline by visit may be explored to evaluate if the effect of the baseline measurement on the timed function test varies over time.

In addition, as described in [Section 6.1.1](#), PPAS will be used to assess the sensitivity of the primary efficacy analysis result using FAS.

A summary plot of the cumulative percent of patients with a percent change from baseline on 4SC time less than a given set of thresholds (from <0% to <100%) will also be produced by sequence at Week 49 and at Week 97.

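### The primary 4-stair-climb model shares one baseline slope across all visits and omits the randomisation stratum: the test stays valid, but Week 49 precision may be lost

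*SAP*

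**What the plan says.** For the primary model, SAP 6.1.1 states: "Covariates for this analysis include the time to climb 4 stairs at baseline, treatment, visit and treatment by visit interaction". SAP 3.4 explains the missing factor: "For the 4 stair climb analysis, the actual baseline value instead of the stratification factor will be included in the model". SAP 5.2 drops the stratum whenever baseline 4SC is in the model, and Protocol 9.2.1 lists the same terms. The choice is open and consistent.

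The only planned look at the form of the baseline effect is in SAP 6.1.2, where an interaction of "baseline by visit may be explored to evaluate if the effect of the baseline measurement on the timed function test varies over time". No planned sensitivity analysis of the primary endpoint adds the stratum or a non-linear baseline term. SAP 6.2, by contrast, puts the stratum into the secondary models alongside the other effects.

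The stratum and the covariate come from the same measurement, the baseline-visit 4SC (Protocol 4.3). Protocol 1.10 gives the reason for the cut: "a prolonged 4SC >8 seconds time is associated with loss of ambulation in 12 months". It names balance between the groups as the purpose of stratifying.

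**The concern.** A model that allows the treatment effect to change by visit but fixes the baseline effect makes a strong assumption in a progressive disease. A boy's starting time may say little about his change at Week 9 and much more about his change at Week 49. With a common slope, the part of the Week 49 relation that is not captured goes into the residual variance at the visit where the primary test is made.

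The stratum raises a related question. A single continuous covariate is naturally read as a straight line on the analysis scale. If the relation bends near 8 s, one slope does not fully use the balance that stratified randomisation provides. At stake are the standard error and the power of the primary test, not its validity.

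**Working it through.** **1. The plan's own figure.** Inputs from Protocol 9.1: "To detect a 2.5 second difference in change from baseline in 4 stair climb", a "standard deviation of 4.0 with 80% power", two-sided 0.05 and 2:1 allocation. Controls needed = 1.5 × (1.960 + 0.842)² × (4.0/2.5)² = 1.5 × 7.849 × 2.56 = 30.1, so 31 controls and 93 boys in a fixed design. With 96 (64:32), a fixed t-test has 81.5% power. With one interim at 50% information and gamma = −1 spending (critical z 2.348, then 2.066), power is 80.4% without futility stopping and 78.5% with it. The stated 96 is reproduced. The formula has no covariate adjustment, so changing the model does not change 96.

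**2. Adding the stratum, Week 49 only.** Simulated ANCOVA, 4,000 runs per scenario, N = 96, effect 2.5 s, total SD held at 4.0, fixed two-sided 0.05. Assumed, because the documents do not give them: 10 to 30% of boys above 8 s, baseline 2.5 to 12 s, slope 0 or 0.3, blocks of 3, and the step sizes below.

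| Step in 4SC change at 8 s | Change in SE | Power gain (points) |
|---|---|---|
| none | up to +0.4% | −0.6 to −0.1 |
| 2.5 s | −0.5 to −1.4% | 0.3 to 1.6 |
| 5 s | −3 to −10% | 1.3 to 3.0 |
| 7.5 s | −9 to −28% | 1.4 to 4.3 |

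Without the stratum, mean estimates are −2.48 to −2.54 for a true −2.5, and power is at least 81.5% throughout. Type I error is 3.5 to 5.6% (Monte Carlo SE about 0.34 points), and 3.5 to 3.9% under the 7.5 s step. The power gain at 7.5 s is held down by a ceiling: with 30% of boys above 8 s and slope 0, power is already 98.6%. A 7.5 s step is also three times the target effect (7.5/2.5).

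A second set (2,000 trials per step, residual SD 3 s) gave squared SE ratios of 0.994, 1.014, 1.074 and 1.180 for steps of 0, 2, 4 and 6 s.

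**3. Adding baseline-by-visit.** Period 1 has six functional visits (Weeks 9, 17, 25, 33, 41 and 49). Let β49 be the true slope at Week 49, γ the fitted common slope and b the baseline time. The fitted Week 49 residual variance is about σ49² + (β49 − γ)² Var(b), so

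information gain ≈ (β49 − γ)² Var(b) / σ49².

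The early visits have the smallest residual SD and dominate γ, so I take γ near the Week 9 slope. Assumed: σ49 = 3.4 s and SD(b) = 2.0 to 2.5 s. Eligibility limits the screening time to 4/1.6 = 2.5 s up to 4/0.33 = 12.1 s.

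- Slope 0.05 to 0.3: 0.25² × (4 to 6.25)/11.56 = 2.2 to 3.4%
- Slope 0.1 to 0.6: 0.50² × (4 to 6.25)/11.56 = 8.7 to 13.5%
- Slope 0.15 to 0.9: 0.75² × (4 to 6.25)/11.56 = 19.5 to 30.4%

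Simulating the mixed model with unstructured covariance (96 boys, complete data, residual SD rising from about 1.3 to 3.4 s, 150 runs) gave 4%, 15% and 36% for these slopes, and a 0.3% loss with no slope. A further run with other assumed slopes and SDs gave about 3 to 25%. There, a stratum main effect alone added only 0 to 3%, because an effect common to all visits cannot follow one that grows.

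**4. How much of step 3 is real precision.** Stratified randomisation already balances the arms on the part of baseline that the stratum explains. The baseline–stratum correlation in step 2 is 0.72 to 0.82, so r² = 0.52 to 0.67. The true excess variance is then about 33 to 48% of what the model reports. A 15% model-based gain corresponds to 15 × 0.33 to 15 × 0.48, or about 5 to 7%. The simulated spread of the estimates improved by about 2%, 7% and 9% in variance (noisy at 150 runs). Most of the gain is removal of an overstated standard error.

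**The case against.** The strongest reply is that the documented 8 s risk does not act through the modelled outcome. A reader might infer from the rationale that boys above 8 s are expected to show an abrupt step in 4SC change. The documents do not say so: they state a higher risk of losing ambulation. A boy who loses ambulation no longer has 4SC collected (Protocol 6 and 7.8) and is missing at later visits; he does not contribute a large increase. SAP 6.1.2 addresses that route with zero velocity, a possible zero-inflated model, a rank test, the proportion unable to climb and time to failure. This stands, and it is why every step size above is an assumption.

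It also stands that the continuous value carries most of the stratum's information, that a straight line is inferred and not stated, and that transformations including the log will be evaluated (SAP 5.2). Subsets cut at 3.5 and 8 s are prespecified (SAP 6.4), and using the continuous value in place of its dichotomy is defensible.

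The reply does not reach the slope common to all visits. Transformation does not make the baseline effect vary by visit, and the subset analyses do not alter the primary standard error.

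**Conclusion.** A minor point of efficiency. A reader might infer that leaving out a stratification factor biases the primary test or inflates its type I error. Neither was found, because the value that defines the factor is in the model; the errors that do arise are conservative.

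The gain is about nil with no step and a constant slope. Otherwise it is modest: at most about 4 points of power from the stratum, with larger SE reductions only under an undocumented 7.5 s step; and roughly 3 to 25% model-based information from baseline-by-visit, beyond that only for the steepest slopes tried. Against 80.4% planned power (78.5% with futility stopping), this is worth having at almost no cost.

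The sizes depend on the assumed steps, slopes, SDs and share of boys above 8 s. The simulations have complete data, so they say nothing about boys who can no longer climb.

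**What to change.** In SAP 5.2 and 6.1.1, make baseline-by-visit a prespecified term of the primary mixed model and remove its optional status in 6.1.2. Add the randomisation stratum, by visit, either in that model or as a committed sensitivity analysis, and reword SAP 3.4 to match. State that the stratum is dropped if a stratum-by-arm cell is empty. Align Protocol 9.2.1: both documents require a major change to the primary analysis to be reflected in a protocol amendment.

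No new data are needed. The cost is a few degrees of freedom. If neither effect exists, the simulated losses are 0.3% for the interaction and 0.6% for the stratum, together 0.9%, or about 1% of information.

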### 3.5. Safety Endpoints

#### 3.5.1. Adverse Events

All adverse events will be reported under the treatment last received prior to the onset of the adverse event.

A 3-tier approach will be used to summarize AEs. Under this approach, AEs are classified into 1 of 3 tiers. Different analyses will be performed for different tiers (See 8.2.3).

Tier-1 events: These are pre-specified events of clinical importance and are maintained in a list in the product's Safety Review Plan (GDMS Location: /Compounds/PF-06/PF-06252616/Product Strategy and Administration/Product Strategy/Safety Review Plan or see link for current version: <http://gdms.pfizer.com/gdms/drl/objectId/090177e18692171a>)

Tier-2 events: These are events that are not tier-1 but are "common". A MedDRA PT is defined as a tier-2 event if there are 4 or more subjects with the same PT in any one treatment group, given the trial will have less than 400 or fewer subjects per treatment group ("Rule of 4").

Tier-3 events: These are events that are neither tier-1 nor tier-2 events. Pfizer standard safety output where all AEs will be included (ie, no new outputs).

Severity is the key baseline information for adverse events. To judge an increase in adverse event severity after dosing, the post-dosing adverse event severity will be compared to the adverse event severity reported prior to the first day of study drug administration.

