### 1.7. Clinical Experience with PF-06252616

The clinical program for PF-06252616 was initiated in June 2012 with a Phase 1 first in human, randomized, double-blind (sponsor and pharmacist unblinded), placebo-controlled study (B5161001) evaluating the safety, tolerability, PK, PD, and pharmacologic (anabolic) effects of escalating single doses of PF-06252616 in healthy adult subjects. The study completed enrollment with 73 subjects at a single site. Doses of 1, 3, 10, 20, and 40 mg/kg administered by IV and 3 mg/kg administered by SC, or placebo were studied. In addition, a repeat IV administration of PF-06252616 10 mg/kg at 2 week intervals over a 28-day treatment period was investigated. Safety was demonstrated at all dose levels and there were no dose-related trends in frequency of reported treatment emergent adverse events.

PF-06252616 serum concentrations in Study B5161001 were measured using a validated enzyme-linked immunosorbent assay (ELISA) method. The PK serum profiles following the single and repeat dose administrations were analyzed. Following either single or repeat IV infused doses, peak concentrations were generally observed within 2 hours after the end of infusion (median  $T_{max}$  was 4 hours after the start of the 2-hour infusion). Concentrations declined relatively rapidly for the first 1 to 2 weeks and more slowly thereafter over a period of months. Following SC administration,  $C_{max}$  was observed at about 1 week (median  $T_{max}$  of 7 days [168 hours]) and concentrations subsequently declined slowly over a period of months. Mean apparent terminal elimination  $t_{1/2}$  was roughly 2 weeks (14 days) overall but appeared to increase with dose, from 12 to 13 days at the lower doses up to 18 to 19 days for the higher doses. Serum  $C_{max}$  generally appears to increase proportionally with dose following IV administration of 1 mg/kg to 40 mg/kg. The apparent bioavailability of the 3 mg/kg SC injection was 61% based on comparison of geometric mean  $AUC_{inf}$  values for 3 mg/kg SC and IV.

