**Sequence 2 (n=35):**

Period 1: Active treatment (PF-06252616) within subject dose escalation (5, 20 and 40 mg/kg)

Period 2: Placebo

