**Sequence 3 (n=35):**

Period 1: Placebo

Period 2: Active treatment (PF-06252616) within subject dose escalation (5, 20 and 40 mg/kg)

Each dose level will be explored in a dose escalating fashion within subjects, starting with the lowest dose. At each dose level, dosing will be administered over a 2-hour IV infusion every 4 weeks for a total of 16 weeks (4 doses). Dose escalation within a subject will occur following review of all available safety data through the planned fourth dose within each dose level. For example, in Period 1, there are three times when individual safety data will be reviewed for a determination of dose adjustment, at Week 13, Week 29 and Week 45 (every 4 months). In Period 2, there are two times when individual safety data are reviewed for a determination of dose adjustment, at Weeks 61 and 77 (every 4 months). Subjects will move from Period 1 to Period 2 without a pause between periods.

[figure not shown]
Subjects who complete this study through Week 97 may be invited to participate in an open-label-extension (OLE) study. Subjects, who have had a positive test result for ADA at any point during the study, *may* be asked to complete additional immunogenicity testing if warranted by other clinical safety findings prior to joining an extension study.

During the study, additional visits will be required to fully characterize PK and safety when subjects would not otherwise be returning for study drug administration. In order to limit the burden of the additional PK/safety assessments, only the first 12 subjects enrolled in the study will be asked to complete these additional PK visits. At each dose level, the first 12 subjects will be asked to return for testing 1 week after the first dose within each level and once again at 1 week after the last dose at each dose level. The additional PK/safety assessments will occur 6 times in Period 1. No additional visits would be required for these subjects in Period 2.

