**Table 3. Period 1 Dosing Schedule**

Dosing Week	1	5	9	13	17	21	25	29	33	37	41	45
Sequence 1 PF-06252616 Dose	5 mg/kg once every 4 weeks				20 mg/kg once every 4 weeks				40 mg/kg once every 4 weeks			
Sequence 2 PF-06252616 Dose	5 mg/kg once every 4 weeks				20 mg/kg once every 4 weeks				40 mg/kg once every 4 weeks			
Sequence 3 Placebo Dose	0 mg/kg once every 4 weeks											

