### **6.7. Visits 7, 13, 19, 24, 28, 32 (Days 85, 197, 309, 421, 533, 645)**

- **Fecal occult blood:** Fecal sample is to be collected at home within approximately 1 week prior to scheduled visit.
- **C-SSRS:** Children's Since Last Visit (Version 6/23/10).

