### **8.2. Reporting Period**

For SAEs, the active reporting period to Pfizer or its designated representative begins from the time that the subject provides informed consent, which is obtained prior to the subject's participation in the study, ie, prior to undergoing any study-related procedure and/or receiving investigational product, through and including 84 calendar days after the last administration of the investigational product. SAEs occurring to a subject after the active reporting period has ended should be reported to the sponsor if the investigator becomes aware of them; at a minimum, all SAEs that the investigator believes have at least a reasonable possibility of being related to investigational product are to be reported to the sponsor.

- AEs (serious and nonserious) should be recorded on the case report form (CRF) from the time the subject has taken at least 1 dose of investigational product through the subject's last visit.

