- Median concentrations at the end of infusion (nominally at 2 hour post start of infusion) against nominal dosing week by Period, Sequence and Dose, as described above for trough concentrations. Individual subject end of infusion concentrations will also be plotted. Linear scale.
- For Sequence 2, Period 2 only (placebo treatment, assessing terminal phase concentrations following active treatment in Period 1), median concentrations will be plotted against nominal time on a semi-log scale. Individual subject concentrations will also be plotted against actual time (all subjects on the same page). Nominal and actual time for these plots will be defined as weeks after the last dose of Period 1 (Week 48).

The range for the x-axes of these plots will be decided on review of the data, and will depend on how long PF-06252616 concentration is quantifiable in the matrix.

For summary statistics and median plots by sampling time, the nominal PK sampling time will be used. For individual subject plots by time, the actual PK sampling time will be used.

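### Complete-study adverse event tables count Sequence 2's residual-drug time after the switch as placebo time: about 6 to 10 weeks per boy, with a modest dilution of the risk difference

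*SAP*

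**What the plan says.** The attribution rule is in SAP 3.5.1: "All adverse events will be reported under the treatment last received prior to the onset of the adverse event". It has no lag and no residual-exposure category. The section refers to an 8.2.3 for the tier analyses, but the SAP has no such section, so no further rule can be found there.

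SAP 6.6.1 presents all AE summaries over both periods together. It compares active treatment, overall and by dose level, with the placebo group using risk differences.

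For Sequence 2 the Protocol (Study Overview, 3.1) gives "Period 2: Placebo", and adds: "Subjects will move from Period 1 to Period 2 without a pause between periods". Protocol Table 3 plans "40 mg/kg once every 4 weeks" for the last four doses of Period 1. The last of these is at Visit 19, Day 309 (Protocol 6.7: "Visits 7, 13, 19, 24, 28, 32 (Days 85, 197, 309, 421, 533, 645"). The first placebo infusion is at Visit 21, Day 337 (Protocol 6.8 and Table 4).

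On persistence of drug, Protocol 1.7 gives a mean terminal half-life of roughly 14 days overall, rising with dose "from 12 to 13 days at the lower doses up to 18 to 19 days for the higher doses", with decline continuing over months. Protocol 2.2.3.3 estimates the terminal half-life after the last Period 1 dose from Sequence 2's Period 2 samples. SAP 6.3.1.4 describes that period as "placebo treatment, assessing terminal phase concentrations following active treatment in Period 1".

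**The concern.** The PK sections treat early Period 2 in Sequence 2 as the tail of active treatment, while the AE section treats the same days as placebo. SAP 6.6.7 goes further and allows the immunogenicity of Process 1 drug material to be assessed from Sequence 2 in Period 2.

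The direction of the error is predictable. A drug-related event that first appears after the switch raises the placebo rate. If the boy had not already had that event on active treatment, it is also missing from the active and top-dose columns. A real harm would look smaller in the tables that describe safety over the whole study.

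**Working it through.** **Inputs**
- Last active dose Day 309, first placebo dose Day 337 (Protocol 6.7, 6.8): gap = 337 − 309 = 28 days.
- Placebo period: Day 337 to Day 673 = 336 days (48 weeks).
- Planned placebo time: 35 boys in Sequence 3 Period 1 and 35 in Sequence 2 Period 2, so 2 × 35 × 336 = 23,520 boy-days.
- Half-lives 12–13, 14 and 18–19 days (Protocol 1.7).
- Washout of five half-lives: an assumption. The Protocol uses this convention for other investigational drugs in exclusion criterion 9. Neither document states a washout for this drug.

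The plan gives no carry-over figure to reproduce.

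**Length of carry-over**

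Days after the switch = 5 × t½ − 28. Share of a boy's placebo period = days / 336. Share of pooled placebo time = 35 × days / 23,520 = days / 672.

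| t½ (days) | 5 × t½ | Ends on Day | Days after switch | Weeks | Share of boy's placebo period | Share of pooled placebo time |
|---|---|---|---|---|---|---|
| 12 | 60 | 369 | 32 | 4.6 | 9.5% | 4.8% |
| 13 | 65 | 374 | 37 | 5.3 | 11.0% | 5.5% |
| 14 | 70 | 379 | 42 | 6.0 | 12.5% | 6.3% |
| 18 | 90 | 399 | 62 | 8.9 | 18.5% | 9.2% |
| 19 | 95 | 404 | 67 | 9.6 | 19.9% | 10.0% |

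The 18–19 day rows apply to boys who ended Period 1 at a higher dose, and the 12–13 day rows to those who ended at a lower one.

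**Rough level at the switch**

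With simple exponential decline, the fraction of the last peak remaining after 28 days is 0.5^(28/t½): 25% at 14 days and 34–36% at 18–19 days. These are upper-end values, because Protocol 1.7 describes a faster fall in the first 1 to 2 weeks.

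**Effect on the risk difference (illustration)**

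Assume true rates of 30% on active and 10% on placebo, and let Sequence 2 carry the active rate for the carry-over share of its placebo period.
- 42 days: Sequence 2 rate = 10 + 0.125 × 20 = 12.5%; pooled placebo = (10 + 12.5)/2 = 11.25%; difference = 30 − 11.25 = 18.75 points.
- 67 days: Sequence 2 rate = 10 + 0.199 × 20 = 14.0%; pooled placebo = 12.0%; difference = 18.0 points.

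The true difference is 20 points, so the loss is 1.25 to 2 points. The illustration holds the active column at 30%, so it leaves out any events lost from that column. It also applies the full active rate while the level is falling, which overstates the contamination of placebo.

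**The case against.** Treatment last received is a pre-specified convention, and a lag is a choice rather than a correction. SAP 6.6.1 calls safety analysis generally exploratory. It also adds tables of the most frequent events by period and/or 4-month interval and permits an exposure-adjusted analysis. SAP 5.2 allows display by sequence, and the E-DMC reviews unblinded safety data throughout. These points stand as mitigation, but none of them reassigns an event. The by-period tables cover only the most frequent events, and the first 4-month block of Period 2 (Days 337 to 449, 112 days) would mix 42 to 67 carry-over days with later time.

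Moving the events into the active column would also bring in weeks of background events. That stands, and is why a separate column is the better remedy.

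A reader might infer more than the documents support:
- **That the primary safety comparison is biased.** Protocol 2.2.1 bases those endpoints on Period 1, by Week 49. They are untouched.
- **That the 84-day SAE window closes at Day 393 and contradicts the AE rule.** Protocol 8.2 runs it "through and including 84 calendar days after the last administration of the investigational product", and Protocol section 5 defines investigational product to include placebo. On schedule the clock starts at Day 645 and ends at 645 + 84 = Day 729. It is also a reporting period, not an attribution rule.
- **That these tables inform exposure in the extension study.** Under Protocol 3.5.1 that level is each boy's own maximum tolerated dose, set by the individual criteria in Table 2. No pooled AE table enters it.
- **That serum levels after the switch can be stated closely.** A one-compartment calculation from the predicted average of 550 µg/mL at 40 mg/kg gives 306–316 µg/mL at the first placebo infusion. The same model gives a peak of about 880–900 µg/mL, against the 1214 µg/mL predicted in Protocol Table 1. It does not fit the Protocol's own figures, so no weight is placed on it.
- **That each event biases the difference twice.** This holds only when the boy's first occurrence falls in the carry-over window.

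**Conclusion.** The point holds for the complete-study and Period 2 AE tables. The rule has no lag, the switch has no pause, and the documents themselves expect drug to be present afterwards. Carry-over is about 6 weeks at 14 days and 9 to 10 weeks at 18–19 days; boys who ended Period 1 on a lower dose would have 4.6 to 5.3 weeks. For half-lives of 14–19 days, 6 to 10% of pooled planned placebo time is carry-over.

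The result is a modest dilution of the active-versus-placebo difference, of predictable direction. It rests on the five-half-life convention and on half-lives from healthy adults given single or short repeat dosing. The size of the dilution also rests on the assumed event rates. It is worth correcting because the remedy is cheap, not because the safety conclusions depend on it.

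**What to change.** In SAP 3.5.1 and 6.6.1:
1. Flag Sequence 2 events with onset from the first placebo infusion up to a pre-specified residual-exposure limit, for example 95 days after the last active dose (five half-lives at 19 days).
2. Show them in a separate post-active washout column, excluded from the placebo column.
3. Add a sensitivity table that uses Sequence 3 Period 1 alone as the placebo reference.

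The cost is one rule in the SAP, a flag derived from dates already collected, one more column, and 6 to 10% less pooled placebo time (10% at the 95-day limit). Treatment, visits and data collection do not change.
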